8.3.4 Safety Endpoints

Assessment of safety endpoints will include:

- All AEs and SAEs

- All deaths.
- All AEs and SAEs occurred during treatment period.
- Vital signs (heart rate, and blood pressure).
- Clinical laboratory assessments from hematology and biochemistry samples.
- Drug exposure.

8.3.5 Further Endpoints of Interest

No further endpoints of interest.

8.4 Analysis Sets

- ***Screen Population***

The screening population will include all subjects who provide written informed consent and who undergo screening assessments, regardless of treatment status in the trial.

- ***Full Analysis Set (FAS)***

- Enrolled
- Presence of measurement at baseline and time point of interest

- ***Per Protocol (PP)***

The per protocol set of subjects is defined as a subset of the FAS analysis set who are compliant with the clinical trial protocol, and is characterized by criteria such as:

- The completion of a certain minimal exposure to the trial drug.
- The absence of any major clinical trial protocol violations.

Major protocol violation will be defined in the Statistical Analysis Plan (SAP).

The PP population will be identified before database lock and will be used to test the primary endpoint as sensitivity analysis..

- ***Safety***

The safety population will include all subjects who received at least one dose of trial treatment.

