5.5 Criteria for Subject Withdrawal

Subjects are free to discontinue the trial at any time without giving their reasons. A subject must be withdrawn in any of the following event:

- Withdrawal of the subject's consent.
- Participation in any other interventional trial during the duration of this trial
- Withdrawal of the Investigational Medicinal Product

If a subject has failed to attend scheduled trial visits, the reasons must be collected and recorded in CRF by investigator as completely and accurately as possible.

In any case, the appropriate Case Report Form (CRF) section must be completed.

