5.5.1 Withdrawal from Trial Therapy

A subject must be withdrawn from trial therapy if any of the following occurs:

- Occurrence of an exclusion criterion which is clinically relevant and affects the subject's safety, if discontinuation is considered necessary by the Investigator and/or Sponsor.
- Therapeutic failure requiring urgent additional drug, or dose adjustment of other drugs that investigator believes would affect the elevation of the safety and/or efficacy, including but not

limited to ACEI, ARB, Statins, β -blockers, CCB, ivabradine, and trimetazidine, also other long-term Chinese traditional medicines for the treatment of CHF.

- Occurrence of adverse events, if discontinuation of trial drug is desired or considered necessary by the Investigator and/or the subject.
- Occurrence of pregnancy.
- Use of a non-permitted concomitant drug, as defined in Section 6.5.2, where the predefined consequence is withdrawal from the IMP.
- Non-compliance.
- Subject withdrew consent
- Subject lost to follow up
- Participation in another clinical trial
- Any events that unacceptably endanger the safety of the subject.

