6.5.2 Prohibited Medicines

NDHP-CCBs, ivabradine, beta receptors agonists and Digoxin (>0.125mg) treatment which may influence the heart control level of Bisoprolol.

Any other additional concomitant therapy that becomes necessary during the trial and any change to concomitant drugs must be recorded in the corresponding section of the CRF, noting the name, dose, duration and indication of each drug.

If the administration of a non-permitted concomitant drug becomes necessary during the trial, e.g., because of AEs, the subject should withdraw from the study, the data should only be used for safety.

The product label should be consulted with regards to combinations not recommended and combinations to be used with caution.

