8.5 Description of Statistical Analyses

8.5.1 General Considerations

Statistical analysis will be performed using CRF data obtained until database lock. The FAS population will be used primarily to present baseline characteristics and analyze efficacy data. Selected efficacy analyses will be repeated for the PP population.

If confidence intervals are to be calculated, 2-sided with significance level 0.05 is used, unless otherwise specified.

Continuous variables will be summarized using descriptive statistics, i.e., number of subject (N), mean, median, standard deviation (S.D.), 25th and 75th percentile (Q1-Q3), minimum and maximum. Counts of missing observation will be included in the denominator and presented as a separate category.

For all variables, the baseline value will be defined as the last measurement taken prior to the first administration of treatment drug.

The dropouts and missing data will not be imputed.

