8.5.2 Analysis of Primary Endpoints

Liner regression will be applied with change from baseline of HR as dependent variable and baseline HR and age as covariates at week 6, 14 and 26, respectively.

Furthermore, the mean value, standard deviation and 95% confidence interval (CI) will be calculated for the difference between HR at baseline and after week 6, 14 and 26 weeks treatment.

This analysis will be done both in FAS population and PP population.

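### Section 6.5.2 and the FAS definition disagree on which heart-rate readings count, and the visit-by-visit complete-case analysis leaves the week-26 estimate open to dropout bias

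*Combined protocol and SAP*

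**What the plan says.** Section 8.4 sets two conditions for the FAS: enrolment and "Presence of measurement at baseline and time point of interest". Membership is thus decided afresh at each visit, and use of a prohibited drug is not a ground for exclusion. Section 8.5.1 makes the FAS the main efficacy set and adds: "The dropouts and missing data will not be imputed".

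Section 8.5.2 fits a separate linear regression at each primary week, "with change from baseline of HR as dependent variable and baseline HR and age as covariates at week 6, 14 and 26, respectively", and reports the mean, SD and 95% CI of the change. Both are repeated in the PP set, of which section 8.4 says: "The per protocol set of subjects is defined as a subset of the FAS analysis set". Section 8.4 leaves to the SAP only the definition of a major protocol violation, which concerns the PP set.

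Section 6.5.2 prohibits NDHP-CCBs, ivabradine, beta agonists and digoxin above 0.125 mg. If one becomes necessary, "the subject should withdraw from the study, the data should only be used for safety".

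Among the events after which a patient must leave the trial, section 5.5 lists "Withdrawal of the Investigational Medicinal Product". Grounds for stopping study drug in section 5.5.1 include "Therapeutic failure requiring urgent additional drug, or dose adjustment of other drugs" and "Occurrence of adverse events, if discontinuation of trial drug is desired or considered necessary by the Investigator and/or the subject". Appendix III schedules vital signs at Visits 1 to 8 and nothing after withdrawal. The 30-day follow-up in sections 7.4.1.3 and 7.4.1.6 is described for adverse events only.

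**The concern.** There are two parts. The first is a conflict of text and needs no assumption. Whether a patient's early readings enter the primary analysis depends on which section the analyst follows. Under a literal 6.5.2, it also depends on something that happened after those readings were taken.

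The second is a weakness that is cheap to repair. Each weekly estimate describes the patients still in the trial at that visit. If withdrawal is related to heart-rate response, those patients are a selected group. Losing poor responders would overstate the reduction, and losing strong responders would understate it. Adjusting for baseline heart rate and age does not remove selection on later heart rate, and a PP subset of the same observed patients cannot test for it. Week 26 is most exposed: it has lost the most patients, and section 8.1 gives neither an expected effect nor a precision for it. Heart-rate change is the only primary endpoint, and section 5.2 says that the trial is meant to inform further studies.

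**Working it through.** **1. The conflict.** Take a patient with valid readings at weeks 6 and 14 who needs ivabradine at week 16.
- Under 8.4 and 8.5.1, the patient counts at weeks 6 and 14.
- Under 6.5.2 read literally, the patient counts at neither.
- If 6.5.2 means only data from the drug onward, the patient counts at both.

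The shift between including and excluding such readings is their share times their mean difference from the rest. Neither is documented. Assuming shares of 2% to 10% and differences of 5 to 10 bpm, the shift is 0.02 × 5 = 0.1 to 0.10 × 10 = 1.0 bpm. The upper end is generous, since 10% would be two-thirds of the planned 15% dropout.

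**2. The plan's own precision.** Section 8.1 gives N = 236, 15% dropout and SD 10 bpm.
- n = 236 × 0.85 = 200.6.
- Half-width = 1.96 × 10/√200.6 = 1.38 bpm at any visit.
- The stated 1.54 (week 6) and 2.12 (week 14) are not reproduced. They need n = (19.6/1.54)² = 162 and (19.6/2.12)² = 85.

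Section 8.1 mentions up-titration status without giving shares. That may explain the gap but does not prove it. I use 1.38 bpm as the yardstick for week 26.

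**3. What a bias requires.** Complete-case bias = dropout share × (mean of stayers − mean of leavers). At 15%, a bias of one half-width needs a difference of 1.38/0.15 = 9.2 bpm.

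**4. Simulation, week 26.** Only the SD of 10 and the 15% come from the documents. Assumed:
- between-visit correlation 0.5 or 0.7; correlation of change with baseline −0.5 and with age 0.1;
- permanent dropout reaching about 5%, 10% and 15% by weeks 6, 14 and 26;
- logistic slopes of 0.25 to 1.25 per 10 bpm (odds ratios 1.28 to 3.49).

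Absolute bias in bpm:

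| | Dropout follows last recorded HR | Dropout follows unrecorded current HR |
|---|---|---|
| Raw mean, reasons split 3:1 | 0.08–0.56 | 0.11–0.65 |
| Raw mean, all one way | 0.18–1.10 | 0.24–1.31 |
| Repeated measures, all one way | 0.01 or less | 0.08–0.41 |

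If opposing reasons balance, raw-mean bias is 0.00–0.02. The near-zero repeated-measures figure under recorded dropout holds by construction, because that is the missing-at-random case. At 236 patients the SD of the estimate is 0.67–0.70 for repeated measures against 0.67–0.72 for the raw mean, so no precision is lost.

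A simpler set-up uses three visits, one 15% dropout before week 26, odds ratios of 2 to 3 and correlations of 0.3 to 0.7. If dropout follows the week-14 change, complete-case bias is about 0.3–1.0 bpm, and about 0 once earlier visits are modelled. If it follows the week-26 change itself, the figures are about 1.0–1.4 and 0.4–1.25.

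**5. Weeks 6 and 14.** One-directional raw-mean bias is 0.03–0.56 and 0.10–0.95 bpm. Against the assumed changes of −3.8 and −7.4, the largest values are 0.56/3.8 = 15% and 0.95/7.4 = 13%.

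**The case against.** On the conflict: 6.5.2 may be a specific rule that overrides a general FAS, or its data may mean only data from the prohibited drug onward. On the latter reading almost no reading is in dispute, because the patient then leaves and no further heart-rate visit is scheduled. Both readings are fair, so the conflict bites only if 6.5.2 is taken literally. But the text does not choose between them, and they can give different primary results.

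On dropout: this is a single-arm exploratory pilot with no success threshold, and the size of any bias rests on assumed inputs. A bias of 1.31 bpm needs leavers to differ by 1.31/0.15 = 8.7 bpm, more than the whole assumed week-14 change of 7.4. That stands, and the upper end should be read as a worst case. The plan also has partial safeguards: counts of missing values (8.5.1), adverse events leading to permanent discontinuation (8.5.4) and recorded reasons for withdrawal (10.2).

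A reader might infer that strong responders are forced out. Section 5.1.1 lists a rate below 55 bpm as intolerance bearing on up-titration, not as a ground for withdrawal, so such patients can stay and be measured. A reader might also take therapeutic failure in 5.5.1 to mean poor heart-rate response. The drugs listed there include ACE inhibitors, statins and trimetazidine as well as heart-rate drugs, so the link is possible but not established.

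Section 8.5.2 does not promise a covariate-adjusted mean, so its silence on covariate values is not a fault. The values need stating only once a model-based mean is reported.

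**Conclusion.** The conflict between 6.5.2 and 8.4 is in the text and should be resolved. The complete-case weakness is real in structure, but its direction and size are unknown. Under the main simulation's assumptions it ranges from about 0 to about 1.3 bpm at week 26, just under one half-width at the extreme. At weeks 6 and 14 it is too small to change the reading.

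The documents do not support the stronger conclusion that the week-26 interval is invalid. Simulated coverage at trial size falls to 62% (recorded) or 52% (unrecorded) only if all dropout runs one way at the strongest slope. It is 94% and 93% at the weakest slope, and 95.7% when strong dropout is balanced. What is at stake is the accuracy of an estimate, not a wrong decision.

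A separate matter should be raised on its own. Section 8.3.1 ties the endpoint to named doses, while 8.4 to 8.5.2 set no dose condition. A reader might infer that this point settles the target as change by visit whatever dose was reached. It does not: the primary objective also speaks of different doses, and the choice is the sponsor's.

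**What to change.** 1. In 6.5.2 and 8.4, state that heart-rate readings taken before the first dose of a prohibited drug stay in the efficacy analysis.
2. Define the FAS once, as treated patients with a baseline heart rate and at least one post-baseline heart rate. Estimate change by visit with one repeated-measures model over Visits 3 to 8: visit, baseline heart rate, baseline-by-visit and age, with unstructured covariance, evaluated at FAS-mean covariates. State the missing-at-random assumption. Keep the planned per-visit means and regressions as supportive.
3. At week 26, add a delta-adjusted sensitivity analysis in both directions. With 15% missing, deltas of 3, 6 and 10 bpm move the mean by 0.45, 0.90 and 1.50 bpm. Tabulate withdrawals by reason.
4. Separately, ask the sponsor to reconcile the dose wording of 8.3.1 with 8.4 to 8.5.2, and show the number of patients at each dose by visit. If a dose-specific target is chosen, item 2 must be adapted to it.

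The cost is a text amendment under section 10.5, a modelling assumption, one stated exception to the no-imputation rule and a little more analysis work. No new data are needed, and treatment and withdrawal rules are unchanged. The model reduces but does not remove bias if dropout follows heart rate that was never recorded, which is why the delta analysis is needed as well.

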8.5 Description of Statistical Analyses

8.5.1 General Considerations

Statistical analysis will be performed using CRF data obtained until database lock. The FAS population will be used primarily to present baseline characteristics and analyze efficacy data. Selected efficacy analyses will be repeated for the PP population.

If confidence intervals are to be calculated, 2-sided with significance level 0.05 is used, unless otherwise specified.

Continuous variables will be summarized using descriptive statistics, i.e., number of subject (N), mean, median, standard deviation (S.D.), 25th and 75th percentile (Q1-Q3), minimum and maximum. Counts of missing observation will be included in the denominator and presented as a separate category.

For all variables, the baseline value will be defined as the last measurement taken prior to the first administration of treatment drug.

The dropouts and missing data will not be imputed.

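### Heart rate at weeks 6, 14 and 26 is analysed in separate complete-case sets, so dropout related to heart rate could bias the estimates in an unknown direction; one repeated-measures model on data already collected is a low-cost improvement

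*Combined protocol and SAP*

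**What the plan says.** - **Analysis sets (section 8.4).** The full analysis set (FAS) consists of enrolled subjects with "Presence of measurement at baseline and time point of interest", so its membership can differ between visits. The only sensitivity set is nested inside it: "The per protocol set of subjects is defined as a subset of the FAS analysis set".
- **Missing data (section 8.5.1).** "The dropouts and missing data will not be imputed".
- **Primary analysis (section 8.5.2).** "Liner regression will be applied with change from baseline of HR as dependent variable and baseline HR and age as covariates", separately at weeks 6, 14 and 26. A raw summary follows: "Furthermore, the mean value, standard deviation and 95% confidence interval (CI) will be calculated for the difference between HR at baseline" and HR at each of those visits. Both are done in the FAS and the per-protocol set. The section does not say at which covariate values the regression is evaluated.
- **Safety summary (sections 8.3.4 and 8.5.4).** Vital signs, including HR, are summarised as mean change with a 95% CI in the safety population, among the patients assessed. This too is an observed-case summary.
- **HR collected (section 7.1, Appendix III).** Resting HR is scheduled at all eight visits. Weeks 3, 10 and 18 serve only as separate secondary endpoints (sections 8.3.2 and 8.5.3).
- **Ways of leaving.** Section 5.5 lists "Withdrawal of the Investigational Medicinal Product" among the events that end participation. Section 5.5.1 stops therapy for, among other reasons, "Therapeutic failure requiring urgent additional drug, or dose adjustment of other drugs" and adverse events. Under section 6.5.2, if a prohibited drug becomes necessary, "the subject should withdraw from the study, the data should only be used for safety".

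**The concern.** Stopping the drug means leaving the trial, so no later HR is scheduled for these subjects. Some exit routes may relate to HR: therapeutic failure may go with too little effect, while adverse events may go with too much. The protocol itself names a resting HR below 55 bpm as possible intolerance (section 5.1.1). Each primary estimate describes only those still present, and the HR that leavers gave at earlier visits is not used for the later primary time points. Weeks 14 and 26 come after more of the attrition than week 6. The size of the HR change is the primary objective (section 4.1), so that figure is what is at stake.

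**Working it through.** **1. The plan's own precision figures.** Inputs from section 8.1: 236 subjects, 15% dropout, SD of change 10 bpm. With n = 236 × 0.85 = 201, the 95% half-width is 1.96 × 10 / √201 = 1.38 bpm at every visit. The plan states 1.54 (week 6) and 2.12 (week 14), which imply (1.96 × 10 / 1.54)² = 162 and (1.96 × 10 / 2.12)² = 85 subjects. Section 8.1 mentions up-titration status without giving a share, and these numbers would fit a count of up-titrated subjects only. The figures are therefore not shown to be wrong, but they leave the target open: HR at the visit, or HR on the named dose.

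**2. What each analysis needs in order to be unbiased.**
- Raw mean: missingness unrelated to HR change.
- Regression at the enrolled mean baseline HR and age: missingness related to HR only through those two covariates. Evaluated at the analysed subjects' own means, least squares returns the raw mean.
- Likelihood repeated-measures model: missingness may depend on any HR already observed, which is a weaker condition.

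**3. Illustration by simulation.** From the plan: 236 subjects, 15% dropout, SD of change 10. Assumed, because the documents are silent: baseline SD 12, slope of change on baseline −0.4, correlation of changes between visits 0.5 or 0.7, no age effect, and monotone dropout driven by the last observed HR. The log-odds of leaving move by 0.5 to 1.5 per 10 bpm, which is an odds ratio of about 1.6 to 4.5. Signs are for subjects with higher HR, or a smaller fall, leaving; they reverse otherwise. A negative value means the fall is overstated.

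Week-26 bias in bpm, raw mean / regression at the enrolled mean baseline:

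| Dropout follows | Correlation | Slope 0.5 | Slope 1.0 | Slope 1.5 |
|---|---|---|---|---|
| HR change | 0.5 | −0.33 / −0.17 | −0.66 / −0.36 | −0.94 / −0.53 |
| HR change | 0.7 | −0.47 / −0.31 | −0.91 / −0.62 | −1.29 / −0.91 |
| HR level | 0.5 | +0.13 / −0.17 | +0.25 / −0.34 | +0.33 / −0.47 |
| HR level | 0.7 | 0.00 / −0.31 | +0.01 / −0.58 | +0.02 / −0.79 |

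At week 14 the regression bias is about two thirds of this. At week 6 neither estimate is off by more than 0.30. The repeated-measures model in all treated subjects stays within 0.03 in every cell.

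**4. Sensitivity to the assumed baseline inputs.** Take dropout on HR level at slope 1.0 and vary baseline SD over 8 to 15 and the change-on-baseline slope over −0.2 to −0.55. The week-26 raw-mean bias then runs from about −0.7 to +1.0 and the regression from about −0.9 to 0. At SD 8 with slopes −0.2 to −0.4 the two err in the same direction. At SD 15, slope −0.55 and correlation 0.7 the raw mean is off by about +1.0 and the regression by almost nothing.

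**5. Where the model does not help, or helps less.** If exit routes cancel symmetrically, all methods are within 0.03. If dropout follows HR not yet observed (15%, inputs of step 3), the model keeps 0.17 to 0.51 bpm at week 26 and the regression 0.27 to 1.08. The raw mean is then off by 0.46 to 1.49 (change) or 0.00 to 0.32 (level), so in the level case it can be closer than the model.

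**6. Scale.** Coverage under a bias b is Φ(1.96 − b/SE) − Φ(−1.96 − b/SE), with SE = half-width / 1.96. For b = 0.75, which is towards the top of the regression range, this gives about 81% at half-width 1.38 and 89% at 2.12.

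**The case against.** Several points on the other side carry weight.

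- **Target.** The primary endpoint names doses as well as weeks (section 8.3.1). If the sponsor means HR on the dose, selection by titration could matter more than 15% dropout, and a by-visit model answers a different question. This stands, and the target must be settled first.
- **Evaluation point.** The regression figures assume the enrolled mean baseline, which section 8.5.2 does not state. At the analysed subjects' means the regression equals the raw mean. This stands as a condition on every regression figure above.
- **Stronger readings.** A reader might infer that the planned result will be biased, that it will overstate the fall, or that the two planned estimates err in opposite directions. The documents support none of these. They give no dropout mechanism, the exit routes may work both ways, and the opposite signs for HR level depend on the assumed baseline SD and slope (step 4).
- **Other planned summaries.** The safety summary of HR may keep subjects whom section 6.5.2 restricts to safety use, so it is a further comparison. It is still observed-case and corrects nothing. Section 8.4 also defers major violations to an SAP; this point is judged on the text available.
- **No imputation.** This is not a defect in itself: a likelihood model imputes nothing either. The gap is that HR from leavers' earlier visits goes unused.
- **Strength of the assumptions.** An odds ratio of 4.5 per 10 bpm applied to every exit is strong, so the upper ends are not expectations.

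**Conclusion.** The point holds as a worthwhile low-cost improvement, not as a fatal flaw. The primary analysis is complete-case at each visit, and nothing in the available text can correct for dropout related to on-treatment HR. If such dropout occurs, week-26 bias is of the order of 0.2 to 0.9 bpm for the regression at the enrolled mean baseline and 0 to 1.3 bpm for the raw mean. These ranges rest on 15% dropout and the assumed inputs of step 3; they are not bounds. Neither the sign nor which planned estimate is closer can be known in advance. Stakes are modest: this is a single-arm exploratory pilot with no threshold to meet, and errors of this size would not reverse a finding that HR fell. Confidence is medium, because the mechanism, correlations and baseline inputs are not in the documents.

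**What to change.** 1. State whether the primary target is HR at the visit or HR on the named dose, and reconcile sections 4.1, 8.1 and 8.3.1 with section 8.5.2.
2. For the by-visit estimate, use one likelihood repeated-measures model in all treated subjects with a baseline HR, with no post-baseline requirement. Take baseline and Visits 3 to 8 HR as responses, visit as a factor, centred age and unstructured covariance with a named fallback. Report week 6, 14 and 26 changes with 95% CI. State that this estimates HR as if leavers had continued, and report deaths beside it.
3. Keep both section 8.5.2 analyses as sensitivity analyses, with the covariate values stated.
4. Add a delta-adjusted analysis at week 26 and amend section 8.5.1 to allow it. A shift of ±5 bpm on missing values moves the estimate by 0.15 × 5 = 0.75 bpm at 15% missing.
5. Tabulate last observed HR and HR change by reason for leaving. Sections 5.5 and 10.2 already provide for recording reasons.
6. Reconcile the safety-only rule of section 6.5.2 with the use of HR recorded before withdrawal.

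The cost is protocol and SAP wording, one standard model, one delta analysis and one table, with no new visits or data. The model still relies on missing-at-random given observed HR and keeps some bias if dropout follows unseen HR. It gains little if dropout is unrelated to HR or the exit routes cancel, and it does not address selection by titration.
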